13.9. Termination of the Study

The Sponsor reserves the right to discontinue the trial at any time. Reasons will be provided in the event of this happening. The PI reserves the right to discontinue the study for safety reasons at any time in collaboration with the Sponsor.

14. STUDY ADMINISTRATION

14.1. Study Monitoring

Arrowhead Pharmaceuticals, Inc. is responsible for assuring the proper conduct of the study about protocol adherence and validity of the data recorded on the eCRFs. Participant confidentiality will be maintained.

In accordance with applicable regulations, cGCP, and Arrowhead Pharmaceuticals, Inc. procedures, Arrowhead Pharmaceuticals, Inc. will be responsible for assigning a study monitor (CRA) who will contact the site to organize a visit prior to participant enrolment to review the protocol and data collection procedures with site staff. In addition, the assigned study monitor will periodically contact the site, including conducting on-site visits. The extent, nature and frequency of on-site visits will be based on such considerations as the study objective and/or endpoints, the purpose of the study, study design complexity, and enrolment rate.

During these site visits, the study monitor will:

- Check the progress of the study
- Review study data collected
- Conduct source document verification
- Identify any issues and address their resolution
- Check investigational product accountability
- Review blood and urine samples and ensure they are labeled and stored correctly

This will be done to verify that the:

- Data are authentic, accurate and complete.
- Safety and rights of participants are being protected.
- Study is conducted in accordance with the currently approved protocol (and any amendments), cGCP and all applicable regulatory requirements.

The PI agrees to allow the monitor direct access to all relevant documents and to allocate his/her time and the time of his/her staff to the monitor to discuss findings and any relevant issues.

At study closure, a study monitor will conduct the following activities in conjunction with the PI or site staff as appropriate:

- Return of all study data to Arrowhead Pharmaceuticals, Inc
- Data queries
- Accountability, reconciliation and arrangements for unused investigational product(s)
- Inventory and final disposition (e.g., destruction, shipping to repository, etc.)
- Review of site study records for completeness

14.2. Quality Assurance

To ensure compliance with cGCP and all applicable regulatory requirements, Arrowhead Pharmaceuticals, Inc. may conduct a quality assurance audit of the study site. Regulatory agencies may also conduct a regulatory inspection of this study. Such audits/inspections can occur at any time during or after completion of the study. If an audit or inspection occurs, the PI and clinical site agree to notify Sponsor as soon as possible following awareness of an impending regulatory inspection. The PI and clinical site agree to allow the auditor/inspector direct access to all relevant documents and allocate his/her time and the time of his/her staff to the auditor/inspector to discuss findings and any relevant issues.

14.3. Records Retention

Following closure of the study, the PI must maintain all site study records in a safe and secure location. The records must be maintained to allow easy and timely retrieval, when needed (e.g., audit or inspection) and whenever feasible, to allow any subsequent review of data in conjunction with assessment of the facility, supporting systems and staff. When permitted by local laws/regulations or institutional policy, some of these records can be maintained in a format other than hard copy (e.g., microfiche, scanned, electronic); however, caution needs to be exercised before such action is taken. The PI must assure that all reproductions are legible and are a true and accurate copy of the original and meet accessibility and retrieval standards, including re-generating a hard copy, if required. Furthermore, the PI must ensure there is an acceptable back-up of these reproductions and that an acceptable quality control process exists for making these reproductions.

Arrowhead Pharmaceuticals, Inc. will inform the PI of the time period for retaining these records to comply with all applicable regulatory requirements. The minimum retention time will meet the strictest standard applicable to that site for the study, as dictated by any institutional requirements or local laws or regulations, or Arrowhead Pharmaceuticals, Inc. standards/procedures; otherwise, the retention period will default to 15 years.

The material to be stored shall include, but is not limited to, the following:

- Signed and dated copy of the final study protocol and any amendments
- Signed and dated letter of IRB approval, letter of constitution of the IRB and copies of any other correspondence relevant to the study with the IRB or regulatory authorities
- The IRB approved Informed Consent Form
- Current *curriculum vitae* (signed and dated) of the PI and co-workers with major responsibilities in the trial
- Site Signature and Delegation of Responsibility Log
- FDA Form 1572 (where applicable)
- Financial Disclosure Form(s)
- Blank CRF/eCRF
- Signed participant informed consent forms
- Laboratory reference ranges (signed and dated)
- The completed CTN Application Form (where applicable)
- The Final Study Report
- Clinical raw data including the Source Data Forms, all clinical laboratory report forms, patient CRFs, drug accountability forms, and dispensing records, etc.

15. INFORMATION DISCLOSURE AND INVENTIONS

15.1. Ownership

[REDACTED]

[REDACTED]

[REDACTED]

15.2. Confidentiality

15.3. Publication

16. APPENDICES

16.1. Definition of Pulmonary Exacerbations (PEx) in CF Patients

A PEx is defined as a new initiation of or change in antibiotic therapy (IV, inhaled, or oral) for any 4 or more of the following signs/symptoms:

- Change in sputum (New or increased)
- Hemoptysis
- Increased cough
- Increased dyspnea
- Increased malaise, fatigue, or lethargy
- Temperature above 38°C (equivalent to approximately 100.4°F)
- Anorexia or weight loss
- Sinus pain or tenderness

- Change in sinus discharge
- Change in physical examination (PE) of the chest
- Decrease in pulmonary function by 10%
- Radiographic changes indicative of pulmonary infection
- Increased respiratory rate or dyspnea at rest

16.2. Guideline for Evaluation and Treatment of Hyperkalemia for NHVs and CF Patients

Hyperkalemia related to renal ENaC inhibition is not expected in this clinical study. However, as a precaution, the following guideline (derived from D B Mount et al., Treatment and Prevention of Hyperkalemia in adults, UpToDate, 2020), is provided to monitor and treat patients with treatment emergent hyperkalemia.

1. Any otherwise unexplained (e.g. no hemolysis) hyperkalemia ($K+ > ULN$ per central lab reference range) will result in:
 - a. Immediate return to clinic or local healthcare provider for repeat $K+$ and ECG. Confirmed hyperkalemia will further result in:
 - i. Patients with $K+ > 6.5$ mmol/L or with any symptoms of muscle weakness or paralysis or new clinically significant cardiac conduction abnormalities on ECG consistent with hyperkalemia (as compared to pre-dose ECG) should result in treatment with therapies to stabilize myocardium, and remove potassium from circulation (intravenous calcium in addition to intravenous insulin and dextrose). Also consider use of diuretics and/or cation exchangers and possibly hospital admission.
 - ii. If potassium is $> ULN$ but < 6.5 mmol/L in the absence of symptoms or ECG findings, treatment for elevated potassium may include only diuretics or cation exchangers. Consider hospital admission.
 - iii. Patient should be followed at least weekly until $K+ < ULN$.
 - iv. Confirmed elevated potassium will result in discontinuation of dosing in the individual patient.

Local labs may be utilized as necessary (including for Screening) if needed by the investigator or for emergent situations, including time critical analytes such as serum potassium and repeat clinical chemistries.

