product, the PI will promptly notify the Sponsor. Laboratory or diagnostic (e.g. ECG) abnormalities will be reported as AEs if considered clinically significant by the PI. Laboratory or diagnostic assessment abnormalities not reported as AEs are not to be reported as Clinically Significant in the study database.

*Any AE consistent with lower respiratory infection, dyspnea, bronchospasm, or CF exacerbation will trigger a chest X-ray and PFT measurement.

Treatment Stopping Rules & Data Safety Committee:

A decision to stop the trial early or discontinue drug in an individual subject or group of subjects **may** be indicated based on any of the following:

1. A single Serious Adverse Events (SAE, defined in Section 11.1) considered at least possibly related to study drug.
2. Two cases of a drop from baseline FEV1 (which must be confirmed on repeat within 48 hours) **in healthy volunteer cohorts** of $\geq 20\%$ (absolute decline in % of predicted) considered to be at least possibly related to study drug by study investigator
3. One case of a drop from baseline FEV1 (which must be confirmed on repeat within 48 hours) **in cystic fibrosis cohorts** of $\geq 20\%$ (absolute decline in % of predicted) considered to be probably related to study drug by study investigator
4. A post-dose increase in serum potassium to > 5.7 milliequivalents/Liter which must be from a non-hemolyzed sample and confirmed by repeat blood draw within 48 hours of initial results.

If any such events occur, within 5 days of Sponsor being notified of the event, the DSC will meet to review the event and determine any necessary actions as detailed below.

Central labs will be utilized. However local labs may be utilized as necessary if needed by the investigator (including for Screening) or for emergent situations, including time critical analytes such as serum potassium and repeat clinical chemistries.

Sponsor or PI can discontinue any subject at any time with or without DSC consultation. If such events (as described above) occur and the subject is not discontinued from the study the reason for not discontinuing the subject will be included in DSC meeting minutes. Including, but not limited to the events listed above, the DSC **may** pause the study to additional dosing or dose escalation to provide time to evaluate safety data and recommend the action to be taken, which may include, but is not limited to one of the following:

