7.4. Stopping Rules & Data Safety Committee

A decision to stop the trial early or discontinue drug in an individual subject, group of subjects or to halt enrollment temporarily or permanently may be indicated based on any of the following:

1. A single Serious Adverse Event (SAE, defined in Section 11.1) considered at least possibly related to study drug
2. Two cases of a drop from baseline FEV1 (which must be confirmed on repeat within 48 hours) **in healthy volunteer cohorts** of $\geq 20\%$ (absolute decline in % of predicted) considered to be at least possibly related to study drug by study investigator
3. One case of a drop from baseline FEV1 (which must be confirmed on repeat within 48 hours) **in cystic fibrosis cohorts** of $\geq 20\%$ (absolute decline in % of predicted) considered to be probably related to study drug by study investigator.
4. A post-dose increase in serum potassium to > 5.7 milliequivalents/Liter which must be from a non-hemolyzed sample and confirmed by repeat blood draw within 48 hours of initial results.

If any such events occur, within 5 days of Sponsor being notified of the event, the DSC will meet to review the event and determine any necessary actions as detailed below. Further dosing of the subject who triggered the stopping rule will be paused until such DSC review occurs.

Central labs will be utilized. However local labs may be utilized as necessary (including for Screening) if needed by the investigator or for emergent situations, including time critical analytes such as serum potassium and repeat clinical chemistries.

The Sponsor or PI can discontinue any subject at any time with or without DSC consultation. If such events (as described above) occur and the subject is not discontinued from the study the reason for not discontinuing the subject will be included in DSC meeting minutes. Including, but not limited to the events listed above, the DSC may pause the study to additional dosing or dose escalation to provide time to evaluate safety data and recommend the action to be taken, which may include, but is not limited to one of the following:

- Discontinuation of a subject or group of subjects from the study
- The study is stopped immediately with no further dosing
- The study will continue until the current cohort is completed
- The study will continue, but the next dose escalation will be to a level midway between the current level and the next planned level
- The study will continue as planned

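### For a confirmed, unexplained post-dose potassium above 5.7 mEq/L, Protocol Section 16.2 makes stopping dosing mandatory while Section 7.4 leaves it to discretion, and nothing says which governs

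*Protocol*

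**What the plan says.** **Protocol Section 16.2** (hyperkalemia guideline, healthy volunteers and CF patients). The trigger is "Any otherwise unexplained (e.g. no hemolysis) hyperkalemia", meaning potassium above the central laboratory's upper limit of normal (ULN). After a repeat test, item 1.a.iv reads: "Confirmed elevated potassium will result in discontinuation of dosing in the individual patient". No DSC review is mentioned.

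**Protocol Section 7.4** (stopping rules). Trigger 4 is "A post-dose increase in serum potassium to > 5.7 milliequivalents/Liter which must be from a non-hemolyzed sample", confirmed by a repeat draw within 48 hours of the initial results. For this and the other three triggers, a decision to "discontinue drug in an individual subject, group of subjects or to halt enrollment temporarily or permanently may be indicated". The DSC meets within 5 days of the Sponsor being notified, and "Further dosing of the subject who triggered the stopping rule will be paused until such DSC review occurs". If such an event occurs and "the subject is not discontinued from the study the reason for not discontinuing the subject will be included in DSC meeting minutes".

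**Protocol synopsis**, stopping rules. The same four triggers are listed, and a decision to "discontinue drug in an individual subject or group of subjects" is again discretionary. The meeting duty is the same: "If any such events occur, within 5 days of Sponsor being notified of the event, the DSC will meet to review the event". The sentence that pauses the subject's dosing is absent, and there is no pointer to Section 16.2.

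**Protocol Section 5.7** names the stopping rules and Section 16.2 together as risk mitigation and does not rank them. **SAP Section 7.1** repeats the discretionary wording and refers back to the protocol.

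**The concern.** One event in one participant appears to have two dosing outcomes. Section 16.2 ends dosing outright. Section 7.4 pauses it and hands the matter to the DSC, which leaves resumption open.

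Hyperkalemia is the risk that Section 5.7 itself attaches to small-molecule ENaC inhibitors, and both provisions are among the stated safeguards in a first-in-human study. If the DSC cannot tell whether it may permit re-dosing after a confirmed trigger, sites and meetings may handle identical events differently. A decision to re-dose could also be a breach of Section 16.2, and Section 13.8 lists failure to comply with dosing requirements as a protocol deviation.

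Reporting is touched too. Protocol Section 12.3 and SAP Section 9.5.1 tabulate adverse events that lead to stopping study drug, so an event reported as an AE could be counted differently depending on which section was followed.

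**Working it through.** The documents give no figure to reproduce, so the check compares the texts and then works one timing illustration.

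| | Section 7.4, trigger 4 | Section 16.2, item 1.a.iv |
|---|---|---|
| Potassium | above 5.7 mEq/L, post-dose | above ULN |
| Sample | non-hemolyzed | otherwise unexplained (hemolysis is the example given) |
| Confirmation | repeat within 48 hours of initial results | repeat at immediate return |
| Effect on the subject's dosing | discontinuation discretionary; pause until DSC review | discontinuation mandatory |
| Reference to the other section | none | none |

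**Step 1: do the triggers overlap?** The potassium grading table in SAP Appendix A sets grade 1 as above ULN up to 5.5 mmol/L, which presumes ULN < 5.5. For potassium 1 mEq/L = 1 mmol/L, so 5.7 > 5.5 > ULN. A confirmed, non-hemolyzed, otherwise unexplained post-dose value above 5.7 meets both triggers.

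**Step 2: where does each rule act?**
- Unexplained, between ULN and 5.7: Section 16.2 alone, so no contradiction.
- Above 5.7 with another explanation: Section 7.4 alone, so no contradiction.
- Above 5.7 and unexplained: both.

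**Step 3: can both be obeyed in the overlap?** If dosing is stopped and the DSC meets, neither section is breached. If the DSC uses its Section 7.4 discretion to let dosing resume, Section 16.2 is breached. The discretion that Section 7.4 appears to give over this subject's dosing is therefore removed by Section 16.2.

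**Step 4: does any text settle it?** Section 5.7 lists both without ranking them, SAP Section 7.1 points back to the protocol, and the synopsis is silent on Section 16.2. The Section 7.4 sentence on minuting a reason concerns leaving the study, not dosing, so it does not settle whether doses resume. The protocol does separate the two elsewhere: under Section 10.6, a participant who becomes pregnant receives no more study drug but may stay in the study.

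**Step 5: how many doses are at issue?** The effect is practical mainly in CF patients, whose later doses come weeks after the first. Take Cohort 6 (doses on Days 1, 15 and 29) with a value above 5.7 at the Day 2 laboratory visit in Table 1.4. The repeat takes 0 days (immediate call-back, Section 10.3.9.1) to 2 days (48 hours, Section 7.4), and the DSC meeting is due within 5 days of notification. Assume a same-day result and same-day notification.

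Review due = sample day + repeat + 5:
- immediate repeat: 2 + 0 + 5 = Day 7, which is 15 − 7 = 8 days before the Day 15 dose;
- repeat at 48 hours: 2 + 2 + 5 = Day 9, which is 15 − 9 = 6 days before it.

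Section 7.4 then leaves up to 3 of 3 doses possible. Section 16.2 leaves 1 of 3, a difference of up to 2 doses.

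Section 7.4 sets no deadline for notifying the Sponsor, so add a delay of d days for result and notification to the Day 9 case:
- 9 + d < 15 holds for d ≤ 5: still up to 3 of 3;
- 9 + d < 29 holds for d ≤ 19: for d = 6 to 19, up to 2 of 3 (Days 1 and 29), if a missed Day 15 dose is not made up.

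The visit-window row of Table 1.4 is hard to align in the available text. If a window of ± 2 days applies to Day 15, the dose could fall on Day 13. The margin is then 13 − 9 = 4 days, and the first bound becomes 9 + d < 13, so d ≤ 3.

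**The case against.** The strongest answer is that the two sections are layered, not opposed. Section 7.4 is a general permission over four kinds of trigger and several levels of action. Section 16.2 is a specific, mandatory rule for one of them. Stopping under Section 16.2 breaches nothing in Section 7.4, which also lets the Sponsor or PI discontinue any subject without consulting the DSC. No sentence in Section 7.4 expressly authorizes re-dosing, and the pause keeps its purpose for the other triggers and for an explained value above 5.7. Section 16.2 is titled a guideline, and it does not say in terms that discontinuation is permanent. Under either section of the body text, dosing stops at least until DSC review.

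Much of this is fair. Stopping does satisfy both sections, the overlap is narrow, and the dose counts rest on assumptions. Reading the Section 16.2 stop as permanent is the natural reading but not an explicit one. The missing pause sentence in the synopsis is an omission, not a contradiction.

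It does not remove the conflict. Section 7.4 expressly covers drug discontinuation in an individual subject and ties that subject's pause to the DSC review. For the overlap subject, Section 16.2 leaves that review nothing to decide about dosing. Item 1.a.iv is mandatory in its wording, although neighboring items advise or permit. The layered reading may be what was intended, but the reader has to supply it, because the documents do not state it.

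**Conclusion.** The concern holds, with high confidence, and should be treated as a must-fix. For a post-dose potassium above 5.7 mEq/L that is non-hemolyzed, confirmed and otherwise unexplained, the protocol gives a mandatory and a discretionary rule on the same participant's dosing, with no order of precedence.

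Its frequency cannot be sized: no event rate is given, and the protocol does not expect hyperkalemia. Its consequence in the Cohort 6 illustration is up to 2 of 3 doses. That rests on a Day 2 event, same-day result and notification, a DSC that permits re-dosing, and a permanent stop under Section 16.2. The illustration shows only that review can fall before the next dose; the contradiction itself does not depend on it. The rank reflects what is at stake, namely re-exposure after a confirmed safety trigger, not the likelihood of the event.

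**What to change.** Reconcile the synopsis stopping rules, Section 7.4 and Section 16.2 so that they state the same dosing action for a subject who meets both triggers, and say explicitly whether DSC review can permit re-dosing. State separately whether such a subject remains in the study, as Section 10.6 does for pregnancy.

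Cross-reference Sections 7.4 and 16.2. This would also point readers of Section 7.4 to the rule that acts between ULN and 5.7. Carry the Section 7.4 pause sentence, or whatever replaces it, into the synopsis. Which rule is right is for the sponsor's clinical team to decide.

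The cost is protocol wording in three places. Sample size, visits, assessments and analysis methods do not change. SAP Section 7.1 defers to the protocol and can stand.

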## List of abbreviations and definitions of terms

Abbreviation or Term	Definition/Explanation
ADA	Anti-drug antibody
AE	Adverse event
AUC0-24	The area under the plasma concentration versus time curve from the zero to 24 hours
AUCinf	The area under the plasma concentration versus time curve from zero to infinity
AUClast	The area under the plasma concentration versus time curve from the zero to the last quantifiable plasma concentration
BAL	Bronchoalveolar lavage
BLQ	Below the limit of quantification
BMI	Body mass index
CF	Cystic Fibrosis
CFQ-R	Revised cystic fibrosis questionnaire
CFTR	CF transmembrane conductance regulator
CI	Confidence interval
Cmax	The maximum plasma concentration
DSC	Data Safety Committee
ECG	Electrocardiogram
eCRF	Electronic case report form
ENaC	Epithelial sodium (Na + ) channel
EOS	End of study
FEV1	Forced Expiratory Volume in the first second
FRC	Functional residual capacity
FSH	Follicle-stimulating hormone
LCI	Lung clearance index
LLOQ	Lower limit of quantification
LOD	Limit of detection
MedDRA	Medical Dictionary for Regulatory Activities
CTCAE	Common Terminology Criteria for Adverse Events
NHV	Normal healthy volunteers
PBO	Placebo
PI	Principal investigator
PK	Pharmacokinetic
ppFEV1	Percent Predicted FEV1
PT	Preferred term
RDD	Respirable delivered dose
SDTM	Standard Data Tabulation Model
SI	International System of Units
SOC	System organ class
t 1/2	The half-life
TEAE	Treatment-emergent adverse event
TESAE	Treatment-emergent serious adverse event
Tmax	The time to maximum plasma concentration
WHODrug	World Health Organization Drug Dictionary

